### 6.1.3 Assessments in Subjects Undergoing On-demand Treatment of Bleeding

Subjects presenting to the study site for an acute bleeding episode will undergo a 30-day observation and follow-up period as outlined below. Throughout the study, subjects may undergo more than one 30-day observation and follow-up periods for treatment of additional bleeding episodes as required until the close of the study. At the end of their study participation, patients will be asked to return for a final Study Completion Visit.

For information on the dose calculation and a definition of minor and major bleeding, see Section 5.4.3. The flow chart of assessments for on-demand treatment is provided on page xxii.

**NOTE:** All adverse events (AEs, see Section 7.4), including thromboembolic events and early signs of allergic or hypersensitivity reactions, occurring between the start of the first *Octafibrin* infusion and the end of each 30-day observation and follow-up period will be recorded. The detection of thromboembolic events will be supported by completing a TEE questionnaire at each study visit for the treatment of bleeding episodes and for surgeries. Concomitant medications will also be recorded throughout each 30-day observation and follow-up period. Administered doses of *Octafibrin* will be recorded for every infusion, including dates, times, and batch numbers.

All SAEs occurring after the first IMP infusion will be documented and reported for a patient throughout the duration of the patient's participation in the study or as required to meet local regulations. Also, any concomitant medications used to treat an SAE will be recorded.

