## 6 STUDY POPULATIONS

### 6.1 Subject Disposition

For the analysis of this study, the following populations will be considered:

Safety Set: All subjects who received at least one infusion of *Octafibrin*. The analysis of safety will be based on this population.

Full Analysis Set: The full analysis set (FAS) defined according to the intention-to-treat (ITT) principle will include subjects who fulfil all of the following conditions:

- received at least one infusion of the IMP.
- entered the study with a confirmed congenital fibrinogen deficiency

Pharmacokinetic analysis set (PK): All patients of the FAS who started the PK assessment and have at least one valid post-baseline fibrinogen activity level.

Pharmacokinetic per protocol analysis set (PK-PP): All patients of the PK analysis set who completed the PK sampling phase without significantly violating the inclusion/exclusion criteria or other aspects of the protocol considered to potentially affect the PK results.

Especially patients will be excluded from this population, if they meet the following protocol deviations:

- Bleeding disorder other than congenital fibrinogen deficiency, including dysfibrinogenaemia
- Any fibrinogen concentrate or other fibrinogen-containing blood product within 2 weeks prior to start of treatment for the PK phase
- Diagnosis or suspicion of a neutralising anti-fibrinogen inhibitor currently or at any time in the past
- Patients who use concomitant medication before or during the PK phase that may confound study results
- Patients who receive less than 90% of the planned dose (nominal)
- Fibrinogen baseline measurement for PK assessment missing
- More than 2 post-baseline blood samples missing for PK assessment

First bleeding analysis set (firstBLEED): subjects of the FAS who have at least one episode of acute bleeding treated with *Octafibrin*.

First bleeding per protocol analysis set (BLEED-PP): All patients from the FirstBLEED analysis set who fulfil the following conditions:

- Provide valid, i.e., non-missing, haemostatic efficacy data for their first bleeding
- Received  $\geq 90\%$  of the planned total dose of the IMP in the first infusion for their first bleeding
- Received  $\geq 80\%$  of the calculated dose (if no dose was calculated, 0% will be assumed) of the IMP over all further infusions of the first bleeding according to the treatment schedule
- Did not meet any of the following exclusion criteria:

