  - Bleeding disorder other than congenital fibrinogen deficiency
  - End-stage liver disease (i.e., Child-Pugh-score B or C)
  - Suspicion of an anti-fibrinogen inhibitor as indicated by previous IVR, if available  $<0.5$  (mg/dL)/(mg/kg)

- Treatment with any fibrinogen concentrate or other fibrinogen-containing blood product within 2 weeks prior to start of treatment for the bleeding episode.
- Did not use any coagulation-active drug (i.e., non-steroidal anti-inflammatory drugs, warfarin, coumarin derivatives, platelet aggregation inhibitors) within 1 week prior to start of treatment for the first bleeding episode, or as a planned or expected medication during the time period from Day 1 until 24 hours (i.e., 1 day) after the last *Octafibrin* infusion

Bleeding analysis set (BLEED): all documented bleeding episodes treated with *Octafibrin* in subjects of the FAS.

Bleeding per protocol analysis set (BLEED-PP): all documented bleeding episodes with no major protocol deviations, i.e. fulfilling the following conditions:

- Fully documented haemostatic efficacy data available for the bleeding
- $\geq 90\%$  of the planned total dose of the IMP was given for the bleeding
- $\geq 80\%$  of the calculated dose (if no dose was calculated, 0% will be assumed) of the IMP was given over all further infusions of the bleeding according to the treatment schedule
- The patient with the respective bleeding did not meet any of the following exclusion criteria:
  - Bleeding disorder other than congenital fibrinogen deficiency
  - End-stage liver disease (i.e., Child-Pugh-score B or C)
  - Suspicion of an anti-fibrinogen inhibitor as indicated by previous IVR, if available  $<0.5 \text{ (mg/dL)/(mg/kg)}$
  - Treatment with any fibrinogen concentrate or other fibrinogen-containing blood product within 2 weeks prior to start of treatment for the bleeding episode.
- The patient with the respective bleeding did not use any coagulation-active drug (i.e., non-steroidal anti-inflammatory drugs, warfarin, coumarin derivatives, platelet aggregation inhibitors) within 1 week prior to start of treatment for the first bleeding episode, or as a planned or expected medication during the time period from Day 1 until 24 hours (i.e., 1 day) after the last *Octafibrin* infusion

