Surgery analysis set (SURG): all documented surgical interventions with a need for at least one infusion of the IMP during the time period from the day of surgery until day of overall clinical assessment of post-operative efficacy in subjects of the FAS.

Surgery per protocol analysis set (SURG-PP): all surgeries of the SURG analysis set, where the patients underwent the surgery fulfil the following conditions:

- Provide valid, i.e., non-missing, intra- and post-operative efficacy data for the surgery
- Received  $\geq 90\%$  of the planned total dose of the IMP in the first infusion prior to the surgery
- Received  $\geq 80\%$  of the calculated dose (if no dose was calculated, 0% will be assumed) of the IMP over all further infusions of the surgery according to the treatment schedule
- Did not meet any of the following exclusion criteria:
  - Bleeding disorder other than congenital fibrinogen deficiency
  - End-stage liver disease (i.e., Child-Pugh-score B or C)
  - Suspicion of an anti-fibrinogen inhibitor as indicated by previous IVR, if available  $<0.5 \text{ (mg/dL)/(mg/kg)}$
  - Treatment with any fibrinogen concentrate or other fibrinogen-containing blood product within 2 weeks prior to start of treatment for the bleeding episode.

- Did not use any coagulation-active drug (i.e., non-steroidal anti-inflammatory drugs, warfarin, coumarin derivatives, platelet aggregation inhibitors) within 1 week prior to start of treatment for the first bleeding episode, or as a planned or expected medication during the time period from Day 1 until 24 hours (i.e., 1 day) after the last *Octafibrin* infusion

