## **7 STATISTICAL ANALYSIS**

The statistical analysis of the primary, secondary and safety endpoints is to be understood in the exploratory sense. No confirmatory hypothesis testing is planned.

The described analyses will be done if the number of patients is appropriate. Especially for the combination of age group and the subpopulations described in section 5.1 a frequency analysis may be replaced by a listing of the relevant data.

The efficacy analysis for the primary endpoint will be performed with the data from the first bleeding event of each patient using the FirstBLEED analysis set (ITT analysis) as the primary population and using the FirstBLEED-PP analysis set (PP analysis) as a secondary population. An additional analysis will be performed for all bleeding events on the BLEED and BLEED-PP population. The primary analysis population for the PK analysis will be the PK-PP population.

Please refer to section 13 for an overview of tables (marked “T”), listings (“L”) and figures (“F”).

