#### 14 TABLES, FIGURES AND LISTINGS (SECTION 14 AND 16.2 OF THE CSR)

The following tables, figures and lists will be generated.

All output will be headed with an appropriate heading specifying study ID and title.

All output will be dated and have page numbers in the form 'Page x of y'.

The order and numbering of the various parts of the Clinical Study Report may not necessarily follow the scheme used below.

All statistical output will identify the underlying analysis populations (see section 6), and indicate the number of subjects/ events in this population (N) and the number of subjects/events actually contributing to the particular output (n).

Due to the small number of patients some of the tables described below may be not generated in the final analysis and replaced by a listing comprising the same variables as in the respective table. If no patient is excluded from the PP population all tables, figures and listings will be done only for the ITT population.

Analysis populations			
14.1.1.1	T	Subject Disposition and analysis populations Number of subjects enrolled, erroneously enrolled, treated, completed, withdrawn	All
14.1.1.2	T	Bleeding episodes Analysis Populations	BLEED
14.1.1.3	T	Surgery Analysis Populations	SURG
14.1.2	L	Protocol Deviations Listing of all major and minor protocol violations together with the reason of violation and exclusion from analysis populations	SAF
14.1.3	L	Compliance to Schedule of PK assessments PK assessments not performed according to the schedule	ITT, PK-PP

Demographic Data			
14.1.4	T	Number of subjects per center, age-group and analysis population	SAF
14.1.5	T	Statistics on age, body height, body weight, body mass index, ethnicity and blood type	ITT, PP
14.1.6	T	Statistics on duration of treatment	ITT, PP
14.1.7	L	Underlying gene defects for FIX and family history of fibrinogen deficiency	ITT, PP
14.1.8	T	FIX activity (%) at screening	ITT, PP
14.1.9	T	Frequency of use of prior and concomitant medications by ATC class (without surgeries) (2 sub-tables: 1 for prior, 1 for concomitant)	ITT, SAF
14.1.10	T	Use of Factor IX concentrates within ½ year before start of study treatment	ITT, SAF

	Bleeding episodes
--	-------------------

14.2.1	T	Subjects included in bleeding analysis (first, minor, major, total) and number of bleedings (minor, major, total)	ITT, PP
14.2.2	T	Number and frequency of bleeding episodes per subject	BLEED, BLEED-PP

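### The SAP section 14 rule for omitting per-protocol output counts patients, but BLEED-PP consists of bleeding episodes, so planned all-bleed per-protocol summaries could be dropped although the two sets differ

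*SAP*

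**What the plan says.** SAP section 14, in the text before the list of outputs, gives a rule for leaving out duplicate output: "If no patient is excluded from the PP population all tables, figures and listings will be done only for the ITT population". The rule counts patients and refers to one PP population.

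SAP section 6.1 defines several PP sets, with different units:

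- First-bleed PP set, made up of patients: "First bleeding per protocol analysis set (BLEED-PP): All patients from the FirstBLEED analysis set who fulfil the following conditions".
- All-bleed PP set, made up of bleeding episodes: "Bleeding per protocol analysis set (BLEED-PP): all documented bleeding episodes with no major protocol deviations, i.e. fulfilling the following conditions".
- Surgery PP set, made up of surgeries: "Surgery per protocol analysis set (SURG-PP): all surgeries of the SURG analysis set, where the patients underwent the surgery fulfil the following conditions".
- PK-PP, made up of patients.

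The first two carry the same label, BLEED-PP, although SAP section 7 and Protocol 9.2.6 call the first-bleed set FirstBLEED-PP.

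SAP section 7 plans the all-bleed per-protocol analysis without any condition: "An additional analysis will be performed for all bleeding events on the BLEED and BLEED-PP population". Protocol 9.2.9 says the same. The output list in SAP section 14 assigns the all-bleed items to both BLEED and BLEED-PP.

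**The concern.** The omission rule and the set it governs use different units. A child can contribute several bleeds, and one of them can leave BLEED-PP while the child stays in through another. In that case the rule's condition is met because no patient is lost, although the per-protocol set is no longer the same as its parent. The planned per-protocol summary is then omitted in a situation where it is not a duplicate.

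What is at stake is a check on a secondary endpoint. SAP 10.4 counts a bleed with a missing efficacy assessment as 'none', that is, as a failure, in the all-bleed analysis. BLEED-PP leaves that bleed out. The per-protocol summary is where a reader would see how much this imputation matters.

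**Working it through.** The plan gives no figure on this point to reproduce, so the check compares units and then illustrates the effect with assumed counts.

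**Step 1. Can a bleed leave while the child stays?** Protocol 6.1.3 allows repeat episodes: "subjects may undergo more than one 30-day observation and follow-up periods for treatment of additional bleeding episodes". In SAP 6.1 the BLEED-PP conditions on efficacy data and dose apply to the individual bleed. So one bleed can fail while another bleed of the same child qualifies.

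**Step 2. When is the rule's condition met?** It depends on which set is checked.

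- If the patient-based first-bleed PP set is checked, excluding a child's first bleed removes that child, and PP output is produced. The rule suppresses output wrongly only when every excluded bleed is a later one.
- If the episode-based BLEED-PP set is checked, the rule suppresses output whenever each affected child keeps at least one qualifying bleed, even if a first bleed was excluded.

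**Step 3. What would be lost?** The all-bleed PP versions, for example items 14.2.14 and 14.2.16 to 14.2.20. When only later bleeds are excluded, the first-bleed tables (14.2.4, 14.2.6, 14.2.8, 14.2.10, 14.2.12, 14.2.13) would be the same in both sets, so nothing is lost there.

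**Step 4. How far can the results differ?** Assume one later bleed has a missing assessment, all other bleeds are successes, and the child has another qualifying bleed. The 95% Clopper-Pearson limits (the SAP's method) for x successes in n are the 2.5% point of Beta(x, n−x+1) and the 97.5% point of Beta(x+1, n−x). The upper limit is 1 when x = n.

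| Assumed treated bleeds | BLEED | BLEED-PP |
|---|---|---|
| 8 | 7/8 = 87.5% (47.3 to 99.7) | 7/7 = 100% (59.0 to 100) |
| 10 | 9/10 = 90.0% (55.5 to 99.7) | 9/9 = 100% (66.4 to 100) |
| 12 | 11/12 = 91.7% (61.5 to 99.8) | 11/11 = 100% (71.5 to 100) |

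**Step 5. How often could it happen?** Assume 6 children with m bleeds each, and an independent exclusion probability q per bleed. The documents give neither m nor q.

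- Check on the first-bleed set: no first bleed excluded and at least one later bleed excluded, (1−q)^6 × [1 − (1−q)^(6(m−1))]. For m = 2 and q = 0.10: 0.531 × (1 − 0.531) = 0.249.
- Check on the episode-based set: no child loses every bleed and at least one bleed is excluded, (1−q^m)^6 − (1−q)^(6m). For m = 2 and q = 0.10: 0.941 − 0.282 = 0.659.

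| m | q | Check on first-bleed set | Check on episode-based set |
|---|---|---|---|
| 2 | 5% | 19.5% | 44.5% |
| 2 | 10% | 24.9% | 65.9% |
| 2 | 20% | 19.3% | 71.4% |
| 3 | 5% | 33.8% | 60.2% |
| 3 | 10% | 38.1% | 84.4% |
| 3 | 20% | 24.4% | 93.5% |

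With one bleed per child both probabilities are 0, because patient and bleed then coincide.

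**The case against.** The strongest reply is that the sentence only means to avoid duplicate output. A statistician would apply it set by set and event by event, and SAP section 7 says the BLEED-PP analysis will be done. That is probably the intent. But nothing in the SAP says the rule works per set or per event. The same introductory text refers to subjects and events together when it defines N and n, whereas this rule names patients only.

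Other parts of the reply stand:

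- The BLEED results are reported in any case. Items 14.1.1.2, 14.1.2, 16.2.3 and 16.2.6.1 would still show the analysis populations, the exclusions and each bleed's assessment. With few bleeds a reader could largely rebuild the per-protocol result, so this is not concealment.
- All analyses are descriptive, so no error rate is affected.

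Three stronger readings are tempting, and the documents do not support them:

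- *The primary PK output could be cancelled.* SAP section 7 states: "The primary analysis population for the PK analysis will be the PK-PP population". SAP section 11 repeats this, and tables 14.2.24 to 14.2.31 are almost all assigned to both PK and PK-PP. Taking full inclusion in a bleeding set as a reason to drop them is strained. If no patient is excluded from PK-PP itself, the two PK sets are the same.
- *Surgical results would disappear.* The planned minimum is 2 surgeries. Surgery characteristics, fibrinogen levels and efficacy are listings, and 16.2.6.3.2 lists the set assignment with reasons for exclusion. Little would be lost.
- *The per-protocol analysis of the primary endpoint is lost.* This follows only if the patient check is made on the episode-based set. The shared label makes that mistake possible, but the plan does not direct it.

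**Conclusion.** The point holds, at minor severity. The omission rule uses the wrong unit for BLEED-PP and does not say which PP set it refers to. Followed literally, it drops the planned all-bleed per-protocol summaries when only later bleeds are excluded and each affected child keeps a qualifying bleed. In the assumed example the untabulated result is 9/9 beside a reported 9/10.

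Under the assumptions of Step 5, the chance of this is roughly 19% to 38% if the first-bleed set is checked, and higher if the episode-based set is checked. These figures illustrate the mechanism and do not forecast this trial. The consequence is limited to a secondary-population summary of a secondary endpoint.

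**What to change.** Replace the sentence in SAP section 14 with:

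> Separately for each pair of sets (PK/PK-PP, FirstBLEED/FirstBLEED-PP, BLEED/BLEED-PP, SURG/SURG-PP), PP output is omitted only if the PP set contains exactly the same units (patients, bleeding episodes or surgeries) as its parent set.

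For this to be unambiguous, the first-bleed PP set in SAP 6.1 should carry the name FirstBLEED-PP that SAP section 7 already uses.

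The cost is one sentence and one label, plus a few extra tables when an episode is excluded. The sponsor's aim of avoiding duplicate output is kept.

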**Appendix I: Determination of slope of elimination curve by non-compartmental PK analysis with WinNonlin®**

The following is taken from the WinNonlin user's guide [1, Chapter 9, pages 218, 219], where K is the rate constant, associated with the terminal elimination phase and the slope of the terminal elimination phase on log scale = - K:

The user may specify the data points to be included in the calculation of K or choose that K not be estimated. If neither of these options is selected, WinNonlin determines the data points to be included, as follows. During the analysis, WinNonlin repeats regressions using the last three points with non-zero concentrations, then the last four, last five, etc. Points prior to  $C_{max}$  or prior to the end of infusion are not used unless the user specifically requests that time range. Points with a value of zero for the dependent variable are excluded. For each regression, an adjusted  $R^2$  is computed:

$$AdjustedR^2 = 1 - \frac{(1 - R^2) \cdot (n - 1)}{n - 2}$$

Where n is the number of data points in the regression and  $R^2$  is the square of the correlation coefficient.

The regression with the largest adjusted  $R^2$  is selected to estimate K with these caveats:

- If the adjusted  $R^2$  does not improve, but is within 0.0001 of the largest adjusted  $R^2$  value, the regression with the larger number of points is used.
- K must be positive, and calculated from at least three data points.
